### **4.2.2 Requirements For NCI protocol #10147 Site Registration:**

Upon site registration approval in RSS, the enrolling site may access OPEN to complete enrollments. The enrolling site will select their credentialed provider treating the subject in the OPEN credentialing screen, and may need to answer additional questions related to treatment in the eligibility checklist.

- A Site initiation visit (SIV) is required for each participating site prior to activation. The local site PI must participate on the call as well as their research nurse, study coordinator,

and pharmacist. To schedule a SIV, please email the Protocol Liaison and [[contact]](mailto:[contact]) and reference the protocol in the subject line of the email.

- Specimen Tracking System Training Requirement:
  - All data entry users (Clinical Research Associate role) at each participating site will need to complete the Theradex-led training.
  - Theradex will provide a certificate of completion, which will need to be submitted to the CTSU through the Regulatory Submission Portal.
  - The training is a one-time only requirement per individual. If an individual has previously completed the training for another ETCTN study, the training does not need to be completed again nor does the certificate of completion need to be resubmitted to the CTSU. However, new versions of the Specimen Tracking System may require new training.
  - This training will need to be completed before the first patient enrollment at a given site.
  - [REDACTED] and [REDACTED] are the main points of contact at Theradex for the training [REDACTED] and [REDACTED], Theradex [contact]).

#### 4.2.3 Submitting Regulatory Documents

Submit required forms and documents to the CTSU Regulatory Office via the Regulatory Submission Portal on the CTSU website.

To access the Regulatory Submission Portal, log on to the CTSU members' website → Regulatory → Regulatory Submission.

Institutions with patients waiting that are unable to use the Regulatory Submission Portal should alert the CTSU Regulatory Office immediately at [name] in order to receive further instruction and support.

#### 4.2.4 Checking Site Registration Status

You can verify your site's registration status on the members' side of the CTSU website.

- Log on to the CTSU members' website
- Click on *Regulatory* at the top of your screen
- Click on *Site Registration*
- Enter your 5-character CTEP Institution Code and click on Go

Note: The status shown only reflects institutional compliance with site registration requirements as outlined above. It does not reflect compliance with protocol requirements for individuals participating on the protocol or the enrolling investigator's status with the NCI or their affiliated networks.

## 4.3 Patient Registration

### 4.3.1 Pre-Registration Procedures

In order to submit the baseline bone marrow aspirate and biopsy and peripheral blood samples, the patient must be pre-registered and assigned a subject ID. The following should be confirmed by the site prior to pre-registering the patient:

- **Informed consent:** the patient must be aware of the neoplastic nature of his/her disease and willingly consent after being informed of the procedure to be followed, the experimental nature of the therapy, alternatives, potential benefits, side-effects, risks, and discomforts. Current human protection committee approval of this protocol and a consent form is required prior to patient consent and registration.
- **Correlative Studies:** bone marrow and/or peripheral blood will be submitted for correlative studies for all patients pre-registered to this study. Note: If the procedure is a dry tap, the patient is still eligible. The peripheral blood must be submitted.

### 4.3.2 OPEN / IWRS

The Oncology Patient Enrollment Network (OPEN) is a web-based registration system available on a 24/7 basis. OPEN is integrated with CTSU regulatory and roster data and with the Lead Protocol Organization (LPOs) registration/randomization systems or Theradex Interactive Web Response System (IWRS) for retrieval of patient registration/randomization assignment. OPEN will populate the patient enrollment data in NCI's clinical data management system, Medidata Rave.

Requirements for OPEN access:

- A valid CTEP-IAM account.
- To perform enrollments or request slot reservations: Be on an LPO roster, ETCTN Corresponding roster, or Participating Organization roster with the role of Registrar. Registrars must hold a minimum of an AP registration type.
- If a DTL is required for the study, the registrar(s) must hold the OPEN Registrar task on the DTL for the site.
- Have an approved site registration for a protocol prior to patient enrollment.

### 4.3.3 OPEN/IWRS User Requirements

To assign an Investigator (IVR) or Non-Physician Investigator (NPIVR) as the treating, crediting, consenting, drug shipment (IVR only), or receiving investigator for a patient transfer in OPEN, the IVR or NPIVR must list the IRB number used on the site's IRB approval on their Form FDA 1572 in RCR. If a DTL is required for the study, the IVR or NPIVR must be assigned the appropriate OPEN-related tasks on the DTL.

Prior to accessing OPEN, site staff should verify the following:

- Patient has met all eligibility criteria within the protocol stated timeframes, and
- All patients have signed an appropriate consent form and HIPAA authorization form (if applicable).

Note: The OPEN system will provide the site with a printable confirmation of registration and treatment information. Please print this confirmation for your records.

Access OPEN at <https://open.ctsu.org> or from the OPEN link on the CTSU members' website. Further instructional information is in the OPEN section of the CTSU website at <https://www.ctsu.org> or <https://open.ctsu.org>. For any additional questions, contact the CTSU Help Desk at [name] or [[contact]](mailto:[contact]).

#### 4.3.4 OPEN/IWRS Questions?

Further instructional information on OPEN is provided on the OPEN tab of the CTSU website at <https://www.ctsu.org> or at <https://open.ctsu.org>. For any additional questions contact the CTSU Help Desk at [name] or [[contact]](mailto:[contact]).

Theradex has developed a Slot Reservations and Cohort Management User Guide, which is available on the Theradex website:

<http://www.theradex.com/clinicalTechnologies/?National-Cancer-Institute-NCI-11>. This link to the Theradex website is also on the CTSU website OPEN tab. For questions about the use of IWRS for slot reservations, contact the Theradex Helpdesk at [contact] or Theradex main number [contact]; [[contact]](mailto:[contact]).

#### 4.3.5 Special Instructions for Patient Enrollment

This Study will use the ETCTN Specimen Tracking System (STS).

- All biospecimens collected for this trial must be submitted using the ETCTN Specimen Tracking System (STS) unless otherwise noted.
- The system is accessed through special Rave user roles: "CRA Specimen Tracking" for data entry at the treating institutions and "Biorepository" for users receiving the specimens for processing and storage at reference labs and the Biorepository.
- Please refer to the Medidata Account Activation and Study Invitation Acceptance link on the CTSU website under the Rave/DQP tab.
- **Important: Failure to complete required fields in STS may result in a delay in sample processing.** Any case reimbursements associated with sample submissions will not be credited if samples requiring STS submission are not logged into STS.

#### 4.4 General Guidelines

Following registration, patients should begin protocol treatment within 3 days.\* Issues that would cause treatment delays should be discussed with the Principal Investigator. If a patient does not receive protocol therapy following registration, the patient's registration on the study may be canceled. The Study Coordinator should be notified of cancellations as soon as possible.

*[\*Note: For leukemia protocols, treatment should be started as rapidly as possible.]*

## 5. TREATMENT PLAN

### 5.1 Agent Administration

Treatment will be administered on an inpatient basis. Reported adverse events and potential risks are described in Section 7. Appropriate dose modifications are described in Section 6. No investigational or commercial agents or therapies other than those described below may be administered with the intent to treat the patient's malignancy. Patient's adherence to oral therapy will be documented through hospital charting.

Arm A : Veliparib 80 mg by mouth twice daily days 1-21. Topotecan 1.2 mg/m^2/d and Carboplatin 150 mg/m^2/day continuous intravenous infusion (CIV) over 5 days for a total of 120 continuous hours on days 3-7.

Arm B : Topotecan 1.6 mg/m^2/d and Carboplatin 150 mg/m^2/day continuous intravenous infusion (CIV) over 5 days for a total of 120 continuous hours on days 1-5.

Regimen Description					
Agent	Premedications; Precautions	Dose	Route	Schedule	Cycle Length
Topotecan	Premedicate with minimum of ondansetron 8 mg IV twice daily	ARM A: 1.2 mg/m  /day in 250 mL D5W ARM B: 1.6 mg/m  /day in 250 mL D5W	IV as continuous infusion over 24 hours for 5 days	Days 3-7*** (ARM A) or Days 1-5*** (ARM B)	28 days: if responding, second cycle can be administered as early as day 28 but no later than day 63. Responding patients may receive up to 3 more cycles (4 total) (see Section 6.1 )
Carboplatin		150 mg/m  /day in 250 cc D5W	IV as continuous infusion over 24 hours for 5 days	Days 3-7*** (ARM A) or Days 1-5*** (ARM B)	
Veliparib**		80 mg	PO twice daily	Days 1-21 (ARM A)	

\*\*Randomized administration.  
\*\*\*Begins at the start of Day 3 or 1 and runs for 5 days continuously, i.e., through the end of Day 7 or 5

### 5.1.1 **Veliparib**

Because there is a potential for interaction of Veliparib with other concomitantly administered drugs, the case report form must capture the concurrent use of all other drugs, over-the-counter medications, or alternative therapies.

Veliparib is not known to be a potent inhibitor of the major human CYPs *in vitro*, indicating a low risk for drug-drug interactions at the proposed dosing concentrations.

### 5.1.2 **Topotecan and Carboplatin**

Carboplatin and Topotecan each have 24 hour stability information described in literature(carboplatin) or package insert (Topotecan). Additionally, Topotecan and Carboplatin were tested in a Simulated Y-site administration using glass vials for a study period of 4 hours. The volume past the Y site is about 5 mL and at the current rate (500 mL over 24 hrs = 21 mL/hr), the drugs will only be in the line together for ~ 15 minutes. This is much less than the 4 hour study period and the agents should be stable through this period. No special premedications are required for these agents except for anti-emetics described in section 5.1 & 5.1.2. Topotecan is a mild irritant, and subjects will be monitored closely for extravasation during administration.

## **5.2 General Concomitant Medication and Supportive Care Guidelines**

### 5.2.1 **Antiemetics**

Antiemetics will be used according to standard practices with a minimum of ondansetron 8 mg IV (or equivalent) twice daily starting prior to topotecan/carboplatin through completion of topotecan and carboplatin.

### 5.2.2 **Hyperuricemia prophylaxis**

To prevent the occurrence and complications of tumor lysis-induced hyperuricemia, all patients without known allergy will receive Allopurinol 300 mg daily orally 24 hours prior to beginning veliparib and continuing through the period of maximal tumor lysis (at least through Day 8).

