## 6. DOSING DELAYS/DOSE MODIFICATIONS

### 6.1 Dosing Delays

Once a cycle is started, prescribed therapy will not be delayed. Patients unable to take veliparib due to toxicity will have those doses skipped.

For patients achieving CR, CRI, PR, or MR following cycle 1, a repeat cycle of the same regimen may be administered beginning no sooner than Day 28 of the preceding cycle and no later than Day 63 from the initiation of the previous cycle (see **Section 5.1**). Delays beyond day 63 should be reviewed with the principal investigator and may be approved if patient is deemed be achieving clinical benefit.

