9.3.6.2 Site(s) Performing Correlative Study: [REDACTED] laboratory, Mayo Clinic

## 10. STUDY CALENDAR

Baseline evaluations are to be conducted within 1 week prior to start of protocol therapy. Baseline labs must be repeated if done greater than 7 days prior to C1D1. In the event that the patient's condition is deteriorating, laboratory evaluations should be repeated within 48 hours prior to initiation of the next cycle of therapy.

	Pre-Reg	Pre-Rand	Day1-7								Day 8-13	Day 14 (± 2d)	Day 15-22 (+/- 2d)	Recovery assessment (day 28-42)
Veliparib ARM A			A	A	A	A	A	A	A	A	A		A	A
Topotecan/Carboplatin ARM A					A	A	A	A	A					
Topotecan/Carboplatin ARM B			B	B	B	B	B							
Informed consent	X													
Demographics		X												
Medical history		X												
Concurrent meds		X			X-----X									
Physical exam		X	X			X					X			
Vital signs		X	X			X					X			
Height		X												
Weight		X	X	X	X	X	X	X	X	X	X			
Performance status		X	X											X
CBC w/diff, plts		X	X	X	X	X	X	X	X	X	X	X	X	
Serum chemistry a		X	X	X	X	X	X	X	X	X	X	X	X	
ECG (as indicated)		X												
Tumor Lysis Labs d		X	X	X	X	X	X				X	X (day 22)		
Adverse event evaluation					X-----X									X
B-HCG			X b											
Bone marrow Aspirate/Biopsy c	X										X e			X
Peripheral blood sample g		X g			X g		X g							
Leukemia mutation panel /Whole exome sequencing sample		X												
RAD51 Assay		X												
Pharmacokinetic blood f		X								X	X	X		
WES peripheral blood for T cells		X												

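### The calendar marks tumor lysis labs on Days 1-5 but not on Days 6-7, the last two days of Arm A's infusion, although lysis prophylaxis runs to about Day 8

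*Combined protocol and SAP*

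**What the plan says.** Section 5.1 staggers the infusions. Arm A receives topotecan and carboplatin "for a total of 120 continuous hours on days 3-7", after two days of veliparib alone; Arm B receives them "for a total of 120 continuous hours on days 1-5". It also states: "Treatment will be administered on an inpatient basis".

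Section 5.2.2 gives allopurinol to every patient without a known allergy, "continuing through the period of maximal tumor lysis (at least through Day 8". Section 5.2.3 allows a phosphate binder on Days 1-8 for patients at risk, to be kept up until lysis has subsided.

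The Section 10 calendar has one row labelled "Tumor Lysis Labs", shared by both arms. Its footnote d lists phosphorus, uric acid, LDH, PT, APTT and fibrinogen. The rows "CBC w/diff, plts" and "Serum chemistry" are marked on every day of the first week. The chemistry footnote (a) includes potassium, calcium, creatinine and BUN but not uric acid, phosphorus or LDH. No footnote or other text sets an arm-specific schedule for the lysis panel or adds it on Days 6-7.

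**The concern.** The prophylaxis sections treat lysis as a live risk until about Day 8, and in Arm A both cytotoxic drugs are still running on Days 6 and 7. Uric acid and phosphorus are the quantities that allopurinol and the phosphate binder are meant to control. If the panel stops after Day 5, they are not scheduled on the last two infusion days of the experimental arm, while Arm B has a panel on every infusion day.

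What is at stake is early recognition of lysis in individual Arm A patients. Nothing in the efficacy analysis depends on it.

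**Working it through.** The plan gives no figure to reproduce. The check is a count of calendar columns.

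**1. Fix the day columns.** Number the row label 0, Pre-Reg 1 and Pre-Rand 2. Arm B's five infusion marks are in columns 3-7 and Arm A's in columns 5-9. Section 5.1 says these are Days 1-5 and Days 3-7. Both rows give the same key: Day 1 = column 3, Day 6 = column 8, Day 7 = column 9. The peripheral blood row for the topoisomerase assay agrees. Its marks are in columns 2, 5 and 7, that is Pre-Rand, Day 3 (just before Arm A's infusion) and Day 5 (48 hours into it), as footnote g describes.

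**2. Read the rows against that key.**

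| Row | Marked columns | Days 6-7 (columns 8-9) |
|---|---|---|
| Topotecan/carboplatin, Arm A | 5-9 | marked |
| Topotecan/carboplatin, Arm B | 3-7 | blank |
| CBC; serum chemistry | 2-13 | marked |
| Tumor lysis labs | 2-7, 11, 12 (labelled day 22) | blank |

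Because CBC and chemistry are marked in columns 8 and 9, the blank belongs to the lysis row and is not a general loss of those two columns.

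**3. Coverage of the infusion**, counting 24 hours per infusion day.
- Arm B: panels on Days 1-5 = 5 of 5 infusion days.
- Arm A: panels on Days 3, 4 and 5 = 3 of 5 infusion days, or 3 x 24 = 72 of 120 hours. Days 6 and 7 have none: 2 x 24 = 48 hours, and 48/120 = 40%.

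**4. Sensitivity to table damage.** The Day 1-7 header spans eight columns (3-10), so the alignment after Day 7 is not settled.
- Header read literally: the next lysis mark (column 11) is in Day 8-13, which is 8 - 5 = 3 to 13 - 5 = 8 days after Day 5.
- Row anchored on its day 22 label and the pharmacokinetic marks: column 11 is Day 14 +/- 2, which is 12 - 5 = 7 to 16 - 5 = 11 days after Day 5.
- Whole lysis row moved one column to the right: the early marks become columns 3-8, or Days 1-6. Day 7 is still blank, Arm A coverage is 4 of 5 infusion days, and 24/120 = 20% of infusion hours have no panel. This reading also removes the Pre-Rand mark.

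The row has only six adjacent early marks, so no shift of the row can cover all seven days.

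**The case against.** The strongest case against has three parts.

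**The table is damaged.** The pharmacokinetic row shows why a row shift is conceivable. It has a Pre-Rand mark for a draw taken only in Arm A, before the arm is known, and moving it one column to the right would fit Section 9.2.1.1 better. The same move on the lysis row would mark Day 6. This stands to the extent that the blank on both days cannot be called certain without the original page. It does not remove the point: the shift would cost the lysis row its Pre-Rand mark, the infusion, CBC and chemistry rows do not need it, and Day 7 would still be blank.

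**There is no contradiction in the text.** A reader might infer that Section 5.2.2 requires lysis labs through Day 8 and that the calendar breaks that requirement. It does not: 5.2.2 sets how long allopurinol is given and says nothing about laboratory frequency. Prophylaxis to Day 8 with panels to Day 5 is a possible schedule. What remains is a mismatch between the period the plan treats as at risk and the period it monitors.

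**The gap is largely mitigated.** Patients are inpatients, potassium, calcium, creatinine and BUN are still scheduled, allopurinol is near-universal, and clinicians can order more tests. No protocol rule acts on the missing values either: Section 6.1 says "Once a cycle is started, prescribed therapy will not be delayed", and the Section 6.3 reductions use creatinine clearance. All of this stands, and it keeps the point minor.

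**Conclusion.** The point holds as a minor safety-monitoring mismatch. On the calendar as it reads, Arm A has a scheduled lysis panel on 3 of 5 infusion days and Arm B on 5 of 5. Under the one-column shift, Arm A would have 4 of 5. The finding rests on the Day 1-7 columns being as the infusion rows show them and on no mark having been lost from the lysis row. The original calendar should settle both.

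Three further inferences go beyond the documents:
- That Day 8 is unmarked. The next mark may fall in the Day 8-13 column.
- That the row was built on Arm B's schedule. It matches that schedule, but nothing says why.
- That the gap distorts the trial's results. Lysis labs do not enter the CR/CRi endpoint, the stratified test or the toxicity stopping events in Section 13.4, so bias, power and the comparison of arms are untouched.

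**What to change.** Check the lysis row against the original calendar. Then, in Section 10, mark tumor lysis labs on Days 6 and 7, at least in Arm A, using the CBC and chemistry draws already marked on those days. Marking both arms is simpler to run and consistent with Section 5.2.2 applying to all patients. If the original has no mark on Day 8, add one there, so that the panel reaches the minimum prophylaxis period.

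Cost, per cycle at full enrollment (40 in Arm A, 60 in total):
- Days 6-7: 2 x 40 = 80 added analyte sets for Arm A only, or 2 x 60 = 120 for both arms.
- With Day 8 as well: 3 x 40 = 120, or 3 x 60 = 180.

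The counts scale with further cycles if the calendar is applied to them. Because patients are inpatients and blood is already drawn on Days 6 and 7, no extra visit is needed. The rest is a wording change to the calendar.

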### 5.2.3 **Hyperphosphatemia prophylaxis**

For individuals at risk for tumor lysis-induced hyperphosphatemia, sevelamer carbonate 800 mg with each meal (or institutional standard) orally day 1-8 can be instituted on admission and continued as tolerated until maximum tumor lysis has abated.

### 5.2.4 **Menstrual suppression**

To achieve menstrual suppression please follow institutional standard practices.

As noted in Section 3.2, women who are pregnant or lactating will not be eligible for this trial, as

the antiproliferative activities of the experimental combination therapy may be harmful to the developing fetus or the nursing infant.

#### 5.2.5 Antibiotic Prophylaxis

Patients will receive prophylaxis directed against gram-negative gastrointestinal infections (GI), candidiasis, and/or herpes simplex virus (HSV), according to individual institutional practices. With regard to GI prophylaxis to prevent local and disseminated aerobic gram-negative infections, the use of moxifloxacin 400 mg by mouth daily (or other quinolone) will begin Day 1 of therapy and continue for the entire duration of profound neutropenia (unless parenteral quinolones are administered). Due to the high risk of typhlitis, prophylaxis with metronidazole 500 mg PO TID should begin day 1, and continue through day 14. In the event of patient allergy or hypersensitivity, institutional standards for antibacterial prophylaxis should be followed. HSV prophylaxis with Acyclovir or Valacyclovir will begin on Day 1 and will continue until absolute neutrophil count exceeds 100/mm^3. Prophylaxis against candidal infections (e.g. posaconazole 300 mg po daily) may be instituted according to institutional practices.

#### 5.2.6 Prevention of perianal mucositis

All patients will receive daily bulk laxatives (e.g., psyllium) and a stool softener (e.g., docusate sodium) unless diarrhea is present, in order to prevent straining at stool and the possibility of perirectal tears.

#### 5.2.7 Need to capture all concurrent medications on case report forms

Because there is a potential for interaction of Veliparib with other concomitantly administered drugs, the case report form must capture the concurrent use of all other drugs, over-the-counter medications, or alternative therapies. The Principal Investigator should be alerted if the patient is taking any agent known to affect or with the potential for drug interactions. The study team should check a frequently-updated medical reference for a list of drugs to avoid or minimize use of. Appendix C (Patient Drug Information Handout and Wallet Card) should be provided to patients if available.

#### 5.2.8 Seizure risk.

Seizures with veliparib were seen in some animal toxicology studies, although at doses much higher than those anticipated for this study. Seizures in animals were successfully treated with lorazepam.

### 5.3 Duration of Therapy

In the absence of treatment delays due to adverse event(s), treatment may continue for 4 cycles (total) or until one of the following criteria applies:

- Failure to meet response criteria of CR, CRi, PR or MR as defined by protocol
- Disease progression
- Intercurrent illness that prevents further administration of treatment
- Unacceptable adverse event(s)
- Patient decides to withdraw from the study
- General or specific changes in the patient's condition render the patient unacceptable for further treatment in the judgment of the investigator
- Patient non-compliance
- Pregnancy
  - All women of child bearing potential should be instructed to contact the investigator immediately if they suspect they might be pregnant (e.g., missed or late menstrual period) at any time during study participation.
  - The investigator must immediately notify CTEP in the event of a confirmed pregnancy in a patient participating in the study.
- Termination of the study by sponsor
- The drug manufacturer can no longer provide the study agent

The reason(s) for protocol therapy discontinuation, the reason(s) for study removal, and the corresponding dates must be documented in the Case Report Form (CRF).

